9.4 End of treatment

The end of treatment is considered the last visit where the decision is made to discontinue treatment. All required procedures might be completed within \pm 28 days of the end of treatment visit. Repeat disease assessment is not required if performed within 28 days prior to the end of treatment visit.

Every effort should be made to complete the end of treatment visit and all required procedures. However, if the subject is unfit or unwilling to return to clinic during the specified time frame, the assessments can be skipped with permission from the Principal Investigator.

Assessments for subjects who have completed protocol therapy and achieved disease control, or have discontinued durvalumab or tremelimumab due to toxicity in the absence of confirmed progressive disease are provided in [Appendix 2](#).

Assessments for subjects who have discontinued durvalumab or tremelimumab treatment due to confirmed PD are presented in [Appendix 3](#).

9.5 Research blood and tumor specimens

For an explanation of the immune related hypotheses and the exploratory analysis plan, see section 14.3. Please see the clinical laboratory manual (Appendix 6) for further details regarding research blood and archival tissue collection.

9.5.1 Research blood

Blood specimens will be obtained for research purposes on cycle 1 day 1, cycle 1 day 14, and cycle 2 day 1 (\pm 4 days). An additional two blood draws at two different time points after cycle 2 day 1 and the last protocol clinic visit are recommended when feasible (as determined by investigator discretion).

Specimens should be collected prior to drug administration. Four (4) tubes of blood are to be collected in BD Vacutainer® CPT™ Cell Preparation Tubes with Sodium Heparin (BD order # 362761 or equivalent) at each research blood draw. Peripheral blood mononuclear cells and plasma will be isolated per institutional practice in the MSK Immune Monitoring Facility (IMF). One EDTA tube should be collected at every research time point for purification of RNA/DNA for TCR analysis and collection of genomic data.

9.5.2 Tumor specimens

For the requirement of submission of pre-treatment tumor tissue, samples collected from fine-needle aspiration, brushing, cell pellet from pleural effusion, bone metastases without a soft tissue component, and lavage are not acceptable. Acceptable samples include transurethral resection of bladder tumor specimens, radical cystectomy specimens, core-needle or excisional biopsies for deep tumor tissue or excisional, incisional, punch, or forceps biopsies for cutaneous, subcutaneous, or mucosal lesions. Representative non-TCC of the urothelial tract FFPE archival tumor specimens (tumor blocks or 30 unstained slides; preference for tumor blocks) must be provided. Patients with < 30 slides may be enrolled after discussion with the principal or co-principal investigators. Biopsy purely for research purposes for this study will not be allowed. Sections should be stored at ambient temperature and protected from light until use or shipment to testing lab by courier at ambient temperature. Samples can be submitted during screening any time after the patient signs the informed consent form up until cycle 1, day 1. Exceptions can be provided by the principal investigator or co-principal investigators.

10.0 EVALUATION DURING TREATMENT/INTERVENTION

A cycle is defined as 4 weeks and includes treatment on day 1 followed by 27 days until the start of the next cycle.

Assessments to be performed at the times stipulated in the table and as clinically required in the management of the patient.	Screening		All assessment to be performed pre-infusion unless stated otherwise		
	Within 28 days	Within 14 days	Cycle 1-4, Day 1 (+/- 4 days)	Cycle 1-4, Day 15 (+/- 4 days)	Day 1 of Cycle 5 onward (+/- 4 days)
Written informed consent	X				
Demography and history of tobacco and alcohol use		X			
Previous treatments		X			
Archival tumor tissue collection ¹	X				
Formal verification of eligibility criteria		X			
Medical and surgical history		X			
Serum pregnancy test ²		X	As clinically indicated		
Durvalumab and tremelimumab co-administration			X		
Durvalumab monotherapy administration					X
Physical examination ³		X	X	X	X
Vital signs (blood pressure, heart rate, respiratory rate, and temperature; pre-, during and post-infusion) ⁴		X	X	X	X
Oxygen saturation (pulse oximetry)		X	X	X	X
Weight		X	X		X
Electrocardiogram (ECG) ⁵		X	X		X
Adverse event/serious adverse event assessment ⁶		X	X	X	X
Concomitant medications		X	X	X	X
ECOG Performance Status		X	X	X	X
CBC (Table 4)		X	X	X	X
Comprehensive chemistry panel (Table 5) ¹⁰		X	X	X	X
TSH ⁷		X	X		X
Coagulation parameters (PTT/PT/INR)		X	As clinically indicated		
Hepatitis B and C; HIV screening	X		As clinically indicated		
Urinalysis (Table 6)		X	As clinically indicated		
Research blood collection ⁸			X (C 1 & 2 only)	X (C1 only)	X
Chest CT ⁹	X				X
CT or MRI of Ab/Pelvis ⁹	X				X ⁹

1. See section 9.5.2 for tumor collection details
2. Pre-menopausal female subjects of childbearing potential only.
3. Full physical examination at baseline; targeted physical examination at other time points
4. Vital signs should be collected before, during, and after the infusion according to the treating investigator's discretion and institutional guidelines and when clinically indicated. Patients will be informed about the possibility of delayed post-infusion symptoms and instructed to contact their study physician if they develop such symptoms.
5. 3 ECG during screening then 1 ECG with prior to each dose.
6. For AE's/SAEs reported during the prescreening additional information such as medical history and concomitant medications may be needed.
7. Free T3 and free T4 will only be measured if TSH is abnormal. They should also be measured if there is clinical suspicion of an adverse event related to the endocrine system.

8. See section 9.5.1 for research blood collection details. Blood specimens will be obtained for research purposes on cycle 1 day 1, cycle 1 day 14, and cycle 2 day 1 (\pm 4 days). An additional two blood draws at two different time points after cycle 2 day 1 and the last protocol clinic visit are recommended when feasible (as determined by investigator discretion).
9. Scans to be performed every 2 cycles (\pm 7 days). See section 10.4 for post-treatment follow up. CT chest may be with or without contrast. MRI of the chest may be performed if patients refuse CT. Abdomen/Pelvis imaging should include IV contrast unless there is an extenuating circumstance approved by the PI or co-PI.
10. It is acceptable to proceed with treatment prior to receipt of amylase and/or lipase results for asymptomatic patients. For subsequently noted grade >3 amylase or lipase levels, study drug/study regimen may be continued at the date of the next scheduled treatment if complete workup shows no evidence of pancreatitis.

10.1 Physical examinations

Physical examinations will be performed according to the assessment schedule. A full physical examination will be performed at screening. Height will be measured at screening only. While on treatment, targeted physical examinations are to be utilized by the Investigator on the basis of clinical observations and symptomatology. Vital signs are to be performed at each assessment. All clinical assessments should occur within \pm 4 days of the intended cycle start date.

10.2 Laboratory Studies During Treatment

Complete blood count (CBC) with differential and platelets and comprehensive panel (Na, K, Cl, CO₂, BUN, Cr, Ca, magnesium, glucose, AST, ALT, total protein, Albumin, ALP, total bilirubin) must be performed on day 1 of each cycle. TSH, LDH, amylase, and lipase will be performed at baseline and on day 1 of each cycle.

10.3 Radiographic Studies During Treatment

Patients will undergo cross-sectional imaging every 2 cycles (\pm 7 days) until lack of clinical benefit. CT chest may be with or without contrast. MRI chest may be performed if patients refuse CT. Abdomen/Pelvis imaging should include IV contrast unless there is an extenuating circumstance approved by the PI. CT scans of the abdomen/pelvis and MRI abdomen/pelvis are both acceptable. Imaging will be evaluated using RECIST v1.1.

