1.0 PROTOCOL SUMMARY AND/OR SCHEMA

This is a phase II study testing durvalumab and tremelimumab in metastatic, non-transitional cell carcinoma of the urothelial tract. Patients with I) any component of small cell carcinoma (or neuroendocrine features) II) predominant squamous cell carcinoma or III) predominant adenocarcinoma of the urothelial tract will be enrolled. A Simon's minimax two-stage design will be carried out. We will enroll 13 patients in the first stage. If we see 1 or more responses in the first stage, we continue to the second stage where we enroll an additional 14 patients for a total sample size of 27 patients. Patients will be treated in 4-week cycles. Patients will receive 4 cycles of the combination of durvalumab and tremelimumab followed by up to 9 cycles of durvalumab maintenance or until lack of clinical benefit or unacceptable toxicity. Cross-sectional imaging will be performed every 8 weeks until the end of treatment. The best, confirmed overall response rate (ORR) by RECIST 1.1 will be determined as the primary endpoint.

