Schedule modification recommendations and toxicity management guidelines for immune-mediated reactions, for infusion-related reactions, and for non-immune-mediated reactions are detailed in Appendix 1. As outlined in Appendix 1, patients may temporarily suspend study treatment for up to 12 weeks beyond the scheduled date of delayed infusion if study drug-related toxicity requiring dose suspension is experienced. If study drug is held because of AEs for > 12 weeks beyond the scheduled date of infusion, the patient will be discontinued from study therapy. Inability to reduce corticosteroid to a dose of ≤ 10 mg of prednisone per day (or equivalent) within 12 weeks after last dose of study drug/regimen will result in study discontinuation. Recurrence of a previously experienced Grade 3 treatment-related AE following resumption of dosing will result in study discontinuation. Patients who discontinue study therapy due to toxicity will be followed as outlined in Appendix 2 or 3. Dose interruptions for reasons other than toxicity, such as surgical procedures, may be allowed. The acceptable length of interruption will be at the discretion of the Sponsor.

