14.3 Secondary Endpoint Justification

1. Safety and tolerability: Adverse events and immune-related adverse events by the current version of Common Terminology Criteria for Adverse Events version 4 (CTCAE v4.03) will be tabulated in order to assess the safety profile and tolerability therapy in treated patients.
2. Progression-free survival (PFS): PFS will be defined as the duration of time from start of treatment to time of recurrence, progression, or death due to any cause, whichever occurs first. Patients will be censored at last follow up date. The Kaplan Meier estimate of median PFS will be reported, as well as the PFS rate at 24 weeks (+/- 1 week).
3. Overall survival (OS): Overall survival will be evaluated using the Kaplan Meier Method.
4. Duration of response (DOR): Duration of response will be determined for each patient with time origin at the first occurrence of confirmed response (CR, PR) until the first occurrence of progression or date of death if the patient dies due to any cause before progression. Duration of response will be evaluated using the Kaplan Meier Method.

5. Clinical benefit rate (CBR): Clinical benefit rate will be defined as the percentage of patients with complete response (CR) + partial response (PR) + stable disease (SD) by 24 weeks from the start of treatment will be reported and the 90% confidence interval will be estimated using exact binomial proportions.
6. Best confirmed ORR, PFS, CBR, and DOR according to immune-related RECIST (irRECIST) as presented by Bohnsack et al.(53) and as proposed in [Appendix 5](#). The methodology is the same as described for RECIST 1.1 except for new lesions do not automatically denote disease progression and the measurement of longest diameter of new measurable lesions are included in the sum of the measurement of the original target lesions. This method accounts for some of the delayed response patterns seen with immune checkpoint blockade. The efficacy endpoints based on irRECIST will be estimated using the same methods for these endpoints based on RECIST.

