
Grade 1 No dose modification
 
Grade 2 Hold study drug/study regimen dose until Grade 2 resolution to Grade ≤ 1. If toxicity worsens, then treat as Grade 3 or Grade 4. Study drug/study regimen can be resumed once event stabilizes to Grade ≤ 1 after completion of steroid taper. Patients with endocrinopathies who may require prolonged or continued steroid replacement can be retreated with study drug/study regimen on the following conditions: 1. The event stabilizes and is controlled. 2. The patient is clinically stable as per Investigator or treating physician's clinical judgement. 3. Doses of prednisone are at ≤ 10 mg/day or equivalent.
	

Appendix 1

Dosing Modification and Toxicity Management Guidelines for Immune-Mediated, Infusion-Related, and Non-Immune-Mediated Reactions (MEDI4736 Monotherapy or Combination Therapy With Tremelimumab or Tremelimumab Monotherapy) - (1 November 2017 Version)

General Considerations

	Dose Modifications	Toxicity Management
Grade 3	Depending on the individual toxicity, study drug/study regimen may be permanently discontinued. Please refer to guidelines below.	immunosuppressive) should be considered for events not responding to systemic steroids. Progression to use of more potent immunosuppressives should proceed more rapidly in events with high likelihood for morbidity and/or mortality – e.g., myocarditis, or other similar events even if they are not currently noted in the guidelines – when these events are not responding to systemic steroids.

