Tumour assessment (CT or MRI)	
For subjects who achieve disease control following 48 weeks of treatment, tumour assessments should be performed every 12 weeks (+/- 14 days) relative to the date of first infusion thereafter until confirmed PD by RECIST 1.1 by investigational site review. Please refer to section 10 and 12 for timings of confirmatory scans.
 
For subjects who discontinue treatment due to toxicity (or symptomatic deterioration), tumour assessments should be performed relative to the date of first infusion as follows: every 8 weeks for the first 48 weeks, then every 12 weeks until confirmed PD by RECIST 1.1 by investigational site review. Please refer to Section 10 and 12 for timings of confirmatory scans.
								

^a Can be collected by phone.

^b Patients with ongoing \geq grade 2 or serious AEs will continue to be followed until the event is resolved to baseline or deemed irreversible or clinically insignificant by the site investigator, or start of new therapy.

^c Free T3 and free T4 will only be measured if TSH is abnormal or if there is clinical suspicion of an endocrine related AE.

Appendix 3

Schedule of study procedures: follow-up for subjects who have discontinued durvalumab and tremelimumab treatment due loss of clinical benefit at the investigator discretion

Evaluation	Time Since Last Dose of durvalumab							
	Day (± 3)	Months (± 1 week)						12 Months and Every 6 Months (± 2 weeks)
	30	2	3	4	6	8	10	
Full physical examination	X							
Vital signs (temperature, respiratory rate, blood pressure, pulse)	X							
Oxygen saturation (pulse oximetry)	X							
Weight	X							
AE/SAE assessment ^{a,b}	X	X	X					
Concomitant medications ^a	X							
Palliative radiotherapy	As clinically indicated							
ECOG performance status	X							
Subsequent anti-cancer therapy ^a	X	X	X	X	X	X	X	
Survival status ^a		X	X	X	X	X	X	X (every 2 months)
Urine hCG or serum β hCG	X							
CBC	X							
Serum chemistry	X							
Thyroid function tests (TSH, and fT3 and fT4 if TSH is abnormal) ^c	X							
Pharmacokinetic assessment, if applicable								
Research blood test	A total of 2 additional research blood draws after the first 3 research blood draws may be performed at the discretion of the study physician							

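### On-treatment scans are counted in cycles, so they can slip with dose holds; this can delay detected progression and bias the 24-week PFS rate upward

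*Combined protocol and SAP*

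**What the plan says.** - Section 10.3: "Patients will undergo cross-sectional imaging every 2 cycles", within 7 days either way. Footnote 9 of the section 10.0 table says the same ("Scans to be performed every 2 cycles"), and section 12.1 also repeats imaging every 2 cycles.
- Section 10.0 defines the unit: "A cycle is defined as 4 weeks and includes treatment on day 1 followed by 27 days until the start of the next cycle".
- Section 1.0 uses calendar time: "Cross-sectional imaging will be performed every 8 weeks until the end of treatment".
- Section 11.1 (schedule modification) allows long holds for drug-related toxicity: "patients may temporarily suspend study treatment for up to 12 weeks beyond the scheduled date of delayed infusion". Beyond that limit the patient stops study therapy. For many immune-mediated events Appendix 1 permits resumption only "after completion of steroid taper", and tapers run for at least 28 days.
- Appendix 2 counts scans from the first infusion for patients who stopped for toxicity: "every 8 weeks for the first 48 weeks", then every 12 weeks. Patients who completed treatment with disease control are scanned every 12 weeks from the same anchor. Appendix 3 also uses the first infusion, with reference to section 10, for patients treated past confirmed progression.
- Section 14.3 reports median PFS "as well as the PFS rate at 24 weeks" (± 1 week). PFS is censored at last follow-up, not at the last scan.

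No section says whether the scan date stays fixed while a dose is on hold before progression.

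**The concern.** Two cycles equal 8 weeks only when every dose is given on time. If a dose is held, the next cycle has no day 1 treatment and so, on the natural reading, has not begun; a site following section 10.3 would move the scan with it. A patient with similar toxicity who discontinues goes onto Appendix 2 and is scanned every 8 calendar weeks. Assessment timing would then depend on toxicity and on whether treatment is held or stopped.

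At stake are the endpoints read in calendar time. A held patient who progresses before week 24, but is next scanned after week 25, counts as progression-free at the landmark. Censoring at last follow-up does not correct this. Duration of response is lengthened in the same way when progression after a response is found late.

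**Working it through.** **The plan's own figure.** The only design calculation is the Simon minimax design for response rate (section 14.2). An exact two-stage binomial search with rates of 5% and 20% returns the stated design: 13 then 14 patients, continue on 1 or more responses, success on 4 or more of 27. Exact type I error is 0.0416 and power 0.8011; the chance of early stopping at a 5% rate is 0.95^13 = 0.513. Scan slippage does not enter this calculation. The plan states no expected value for 24-week PFS.

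**Longest gap.** 8 weeks + a 12-week hold = 20 weeks.

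**How far one steroid-treated event moves a dose.** The taper overlaps the 28-day cycle, so only the part beyond the next due dose (day 29) causes delay. Assume 5 days to improvement and a 28-day taper. Delay = onset day + 5 + 28 − 29 = onset day + 4. Onset on day 1, 10 or 20 delays the dose by 5, 14 or 24 days; 28 days or more needs onset on day 24 or later. Only delays of 7 days or less stay inside the scan window.

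**Effect on 24-week PFS.** Assumptions, none from the documents:
- exponential PFS, median 4 months (17.4 weeks);
- 28% of patients with one hold, unrelated to progression. This share borrows the 28% discontinuation rate of the phase Ib study in section 3.4.3, which is not a hold rate;
- progression found only by scan.

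S(t) = 0.5^(t/17.4), so S(8) = 0.727, S(16) = 0.529, S(20) = 0.451 and S(24) = 0.384. Calendar scans fall at weeks 8, 16 and 24, and a hold then adds nothing. If scans follow the held cycles:

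excess = share held × [S(last scan by week 25) − S(24)]

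| Hold (weeks) | Starts before | Scans (weeks) | Last scan by week 25 | Excess per held patient | Excess at 28% held (points) |
|---|---|---|---|---|---|
| 1 | scan 1 | 9, 17, 25 | 25 | 0 | 0 |
| 2 | scan 1 | 10, 18, 26 | 18 | 0.104 | 2.9 |
| 4 | scan 1 | 12, 20, 28 | 20 | 0.066 | 1.9 |
| 4 | scan 2 | 8, 20, 28 | 20 | 0.066 | 1.9 |
| 4 | scan 3 | 8, 16, 28 | 16 | 0.144 | 4.0 |
| 8 | scan 1 | 16, 24, 32 | 24 | 0 | 0 |
| 8 | scan 2 | 8, 24, 32 | 24 | 0 | 0 |
| 8 | scan 3 | 8, 16, 32 | 16 | 0.144 | 4.0 |
| 12 | scan 1 | 20, 28, 36 | 20 | 0.066 | 1.9 |
| 12 | scan 2 | 8, 28, 36 | 8 | 0.343 | 9.6 |
| 12 | scan 3 | 8, 16, 36 | 16 | 0.144 | 4.0 |

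The largest entry is 0.28 × (0.727 − 0.384) = 9.6 points. Over medians of 2 to 6 months and 10% to 40% held, the range is 0 to 15.2 points, or 0 to 4.1 of 27 patients. The top needs a 2-month median, 40% held and a 12-week hold between scans 1 and 2.

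**Effect on clinical benefit rate.** If stable disease at any scan by week 24 counts, a hold cannot raise the rate. Moving the first scan from week 8 to 12, 16 or 20 lowers it by 10.7, 19.8 or 27.6 points per held patient (median 4 months), and later holds change nothing. It rises, by the PFS amounts, only if the endpoint means not progressed at week 24 with earlier stable disease carried forward, which section 14.3 does not say.

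**The case against.** The strongest reply is that no section says cycles move with holds. A cycle is defined as 4 weeks, two cycles make 8, and section 1.0 says 8. Appendix 3 even ties section 10 scans to the first infusion in patients still on treatment. This stands in part: slippage is the natural reading, not a stated rule, and a reader would be wrong to infer that the calendar anchor exists only for patients off treatment. It does not close the gap. Appendix 3 covers patients whose progression is already confirmed, and it points to a section that contains no such anchor.

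A reader might also infer that every steroid-treated event moves scans by at least 4 weeks. The documents do not support that floor: the taper overlaps the cycle, and non-immune Grade 3 events can resume within 7 to 14 days. Some toxicities never enter the gap, because Appendix 1 requires permanent discontinuation (Grade 3 or 4 pneumonitis or nephritis) or allows treatment to continue (isolated hypothyroidism).

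The PFS figures are fairly called upper bounds. Deaths count as events, and section 12.1 has patients examined for progression every cycle. PFS and clinical benefit are descriptive secondary endpoints in a single arm; no test depends on them, and no comparison of held with discontinued patients is planned.

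**Conclusion.** The point holds as an unresolved conflict that lets scan timing depend on toxicity. The 24-week PFS rate can be biased upward and duration of response distorted. The size is 0 to roughly 10 points in plausible cases and about 15 at the extreme. It rests on assumed exponential PFS, assumed hold rates and scan-only detection, and it can be zero, as with an 8-week hold before the first or second scan. It would be tempting to say that the clinical benefit rate is inflated too; the wording of section 14.3 does not support this, and the rate may be distorted in either direction or not at all. The primary response-rate design is unaffected. This is a cheap improvement.

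**What to change.** In footnote 9 of section 10.0, section 10.3 and section 12.1, replace the cycle count with: on-treatment scans every 8 weeks (± 7 days) from the date of first infusion, regardless of dose holds or delays; during retreatment, from the first retreatment dose. Reconcile this with section 1.0, the cycle definition in section 10.0, Appendix 2 (which changes to every 12 weeks after week 48 once treatment has stopped) and Appendix 3. Dosing rules are untouched.

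The cost is a short amendment. Patients without holds keep the same schedule. A 12-week hold extends treatment by 12/8 = 1.5 scan intervals, so patients with long holds may have one or two additional scans.
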